**Data: 10/10/2018**

## **INTRODUCTION**

It is well known that female pelvic floor weakness and/or pelvic floor dysfunction (PFD) can have both structural and functional effects, such as urinary incontinence, bowel incontinence, pelvic organ prolapse, and dyspareunia and/or sexual dysfunction (Bozkurt et al., 2014, Pierce et al., 2015, Hyakutake et al., 2016, Neels et al., 2016). One of the main risk factors associated with pelvic dysfunction is the reproductive process, including pregnancy and birth. During this process both modifiable and non-modifiable risk factors for PFD can be identified. Chief among the former are the pregestational and full-term body mass index (BMI), weight gain, smoking, the type of birth, the use of forceps, the duration of the first and second stages of birth, the practice of episiotomy and the use of epidural anaesthesia. Among the non-modifiable risk factors (also known as risk indicators), are age at maternity, position of the foetus and circumference of the newborn's head, the weight of the newborn, and the presence/existence of perineal injury, chiefly those which can affect the anal sphincter (Bozkurt et al., 2014, Hyakutake et al., 2016).

Of all these factors, vaginal birth is the chief modifiable risk factor for developing pelvic floor dysfunction, as women in this group are 2.8 times more likely to suffer stress urinary incontinence, and 5.5 times more likely to suffer a prolapse of the pelvic organs, in comparison with those who give birth via caesarean section. These risks increase with instrumental delivery, which seems to be related to the fact that the incidence of injury to the anal musculature is higher in this procedure (Howard & Makhlouf, 2016).

Among the non-modifiable obstetric risk factors, chief is perineal trauma, whether spontaneous or induced (second degree tears or obstetric anal sphincter injuries), which represents one of the most frequent complications associated with birth (85% of puerperal women) (León-Larios et al., 2017), and has a clear influence in the subsequent appearance of PFD (Bose et al., 2017, León-Larios et al., 2017).

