## **THE STUDY**

### **Aim**

The aim of this study is to evaluate the influence of Pilates sessions during pregnancy on the incidence and degree of intrapartum perineal injuries.

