### **Interventions**

The study will be carry out in two stages: the first involved finding Pilates trainers to deliver the sessions, while the second collated participant data from both the experimental and control groups. The first phase took place in November 2018, with the collaboration of two trainers in Huelva and one in Seville, all with the same training background. The second phase will be carried out between December 2018 and December 2019 in the corresponding health centres in Huelva and Seville.

In order to eliminate potential bias as a result of the antenatal classes being deliver by health professionals of different categories, only those health centres where classes are deliver by a midwife were selected for the study. The women participat in the corresponding antenatal classes at the respective centres were

then will be invited to participate in the study either to the experimental group (AC + PM) or in the control group (AC only).

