#### **Sample size**

A minimum sample size of 36 women will be projected, for a confidence level of 95% and a power of 80%, considering 49% avoiding episiotomy in the control group in comparison with 98% in the experimental group (Rodríguez et al., 2017), and divided according to a ratio of 2 women in the control group for every woman in the experimental group. This number will increase in case any women dropped out, such that the final number of participants will be 72, of which 24 will be from the experimental group and 48 the control.

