#### **Data Collection**

##### Outcomes

The dependent variables will be age (years), blood pressure (mmHg), weight (kg), BMI (kg/m^2), starting level of physical activity, and tobacco use. These variables will be all measured by experienced personnel at the start of the experimental phase, at two weeks, and again at four weeks after the treatment for both groups had been completed.

Variable relating to childbirth will be measured between the eighth and tenth day after birth by telephone interview and review of hospital medical history. The number of weeks of pregnancy at birth will be measured on a discrete

quantitative scale. Labour onset (spontaneous, stimulated, induced), type of delivery (spontaneous, assisted delivery with forceps, Thierry's spatulas or vacuum extraction, caesarean section), the use of intrapartum pharmacological analgesia (none, epidural anaesthesia, sedatives, nitrous oxide), type of episiotomy (not required, median, lateral, medio-lateral) will be measured by nominal scales, while the degree of perineal tear will be evaluated on an ordinal scale (no injury, degree I: injury to perineal skin; degree II: injury to perineal skin and muscle; degree III: injury to perineal skin, muscle and anal sphincter; degree IV: injury to perineal skin, muscle, sphincter and anorectal mucosa). Weight (kg) and height (cm) will be recorded during the routine antenatal appointments at the health centres using stadiometers with weight scale function. The level of physical activity will be measured using the International Physical Activity Questionnaires (IPAQ) (Craig et al. 2003).

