#### **Data analysis**

The quantitative variables will be presented with the mean and standard deviation, while the qualitative data will be given in frequencies and percentages.

In order to measure the goodness of fit of the quantitative data to a normal distribution, a Lilliefors corrected Kolmogorov-Smirnov test will be used. Bivariate analysis will be carried out with Student's t-test for the comparison of two means. In the case of the qualitative data, the Chi-square test will be used, except when Fisher's exact test was required. Likewise, for the analysis of three or more means, a repeated measures ANOVA will be used to evaluate the effects of the

treatment in the two groups, at baseline, three and five weeks. Correlation between the quantitative variables will be verified using the Pearson coefficient correlation ( $r$ ). Finally, in order to allow for the possibility that the data did not meet the criterion of normality or homoscedasticity, non-parametric versions of the tests above will be also carry out.

Binary logistic regression models adjusted for various qualitative and quantitative predictive variables will be calculated in order to determine association of the variables with perineal trauma in childbirth.

The Odds Ratios (ORs) will be determined with a confidence interval of 95%. The goodness of fit tests ( $-2 \log$  likelihood, goodness of fit statistic, Cox and Snell  $R^2$ , Nagelkerke  $R^2$  and Hosmer–Lemeshow) will be calculated to evaluate the overall fit of the model.

In all statistical analyses, alpha will be set to below 5% / the significance level was established at 5% ( $p < 0.05$ ) and a confidence interval of 95% will be computed. All statistical calculations will be made using IBM SPSS Statistics version 25.0.

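### The only adjusted analysis is an open-ended ordinary logistic model in 24 versus 48 non-randomised women: pre-specify a short model and fit it by Firth penalised likelihood

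*Combined protocol and SAP*

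**What the plan says.** Data analysis: "Binary logistic regression models adjusted for various qualitative and quantitative predictive variables will be calculated", to find associations with perineal trauma, and "The Odds Ratios (ORs) will be determined with a confidence interval of 95" per cent. The section gives no predictor list, no cap, no selection rule and no provision for sparse cells. It does not define the binary outcome, name study group as a term or state the interval method. Its other analyses (t-tests, chi-square or Fisher, repeated-measures ANOVA, correlation, non-parametric versions) are not described as adjusted.

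Two readings of the outcome are open. The Aim concerns the "incidence and degree of intrapartum perineal injuries", and the Introduction calls perineal trauma "one of the most frequent complications associated with birth (85% of puerperal women"). Sample size is built on episiotomy, "considering 49% avoiding episiotomy in the control group in comparison with 98% in the experimental group", with a final split in which "24 will be from the experimental group and 48 the control".

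Allocation is by invitation: women "will be invited to participate in the study either to the experimental group (AC + PM) or in the control group (AC only"). Outcomes lists six variables measured at the start ("age (years), blood pressure (mmHg), weight (kg"), BMI, physical activity and tobacco use), followed by childbirth variables such as labour onset, type of delivery and analgesia.

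**The concern.** The groups are not randomised, so readers will look to the adjusted odds ratio and its interval for a comparison that allows for differences between the women. Two problems could distort that result.

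- **Empty cell.** If the outcome is episiotomy and Pilates works as assumed, the Pilates arm may have no events. Ordinary logistic regression then has no finite estimate for group.
- **Too many predictors.** If the outcome is any injury, uninjured women are the scarce class. A long list pushes the maximum-likelihood odds ratio away from 1 when there is a true effect, and makes ordinary likelihood-ratio inference too liberal.

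The fit statistics that the plan lists (such as Nagelkerke R² and Hosmer–Lemeshow) remedy neither.

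**Working it through.** **The plan's own figure.** Rates 0.98 and 0.49, ratio 2:1, two-sided 5% (assumed), 80% power. Pooled rate = (0.98 + 2 × 0.49)/3 = 0.6533.

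n = (A + B)² / 0.49² = 8.91, where A = 1.96√(1.5 × 0.6533 × 0.3467) and B = 0.8416√(0.98 × 0.02 + 0.49 × 0.51/2).

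With continuity correction: (8.91/4)[1 + √(1 + 6/(8.91 × 2 × 0.49))]² = 11.77, so 12 + 24 = 36. This matches the plan; the sample size is not in dispute.

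**Reading 1: episiotomy, with group as a term.** Rates are 1 − 0.98 = 2% and 1 − 0.49 = 51%. Expected events: 0.02 × 24 = 0.48 and 0.51 × 48 = 24.48, together 24.96. The chance of no Pilates event is (1 − p)^24. Coverage of the 95% interval comes from enumerating all 25 × 49 tables, without covariates, with control at 51%:

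| Pilates rate | No Pilates event | Wald coverage, no empty cell | Ordinary profile | Firth profile |
|---|---|---|---|---|
| 2% | 61.6% | 89.8% | 98.4% | 95.3% |
| 5% | 29.2% | 95.6% | 96.7% | 96.6% |
| 10% | 8.0% | 96.7% | 91.4% | 96.4% |
| 15% | 2.0% | 96.9% | 93.9% | 95.4% |

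Example, 0/24 versus 24/48. Ordinary maximum likelihood gives an odds ratio of 0, with a profile upper limit of 0.09. In a 2 × 2 table Firth amounts to adding 0.5 to each cell: odds of 0.5/24.5 against odds of 24.5/24.5, a ratio of 0.020, with penalised-profile interval 0.0002 to 0.16.

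With 3, 6 and 12 covariates (simulation described below), ordinary profile coverage is 98, 98 and 89% at 2% versus 51%, and 91, 90 and 85% at 10% versus 51%. Firth gives 95, 96 and 96% at the first pair of rates, and 96% throughout at the second.

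**Reading 2: any injury.** The 85% is a literature figure in the Introduction, used here as an assumption. Uninjured women: 0.15 × 72 = 10.8. Per parameter (group plus 3, 6 or 12 covariates): 10.8/4 = 2.7, 10.8/7 = 1.5, 10.8/13 = 0.8. The chance of an empty group-by-outcome cell is about 2%.

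Simulation: 5,000 trials per scenario, 24 versus 48, with covariates assumed independent and without effect. Six is the number of baseline variables under Outcomes; 12 is an assumed long list. Assumed rates are 70% versus 85%, so the true odds ratio is 0.70/0.30 divided by 0.85/0.15, which is 0.41.

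| Covariates | ML median | Firth median | Wald coverage | Ordinary profile | Firth profile |
|---|---|---|---|---|---|
| 3 | OR 0.38 | OR 0.41 | 96% | 94% | 96% |
| 6 | OR 0.37 | OR 0.42 | 95% | 93% | 96% |
| 12 | OR 0.30 | OR 0.41 | 92% | 87% | 95% |

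Range over the assumed Pilates rate (ML medians for 3, 6 and 12 covariates): at 60%, where the truth is 0.26, ML gives 0.24, 0.22 and 0.16; at 75%, where the truth is 0.53, ML gives 0.50, 0.49 and 0.41. Firth stays within 0.01 of the truth in both.

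Type I error at 85% in both arms, with 3, 6 and 12 covariates: ordinary likelihood ratio 7.6, 7.9 and 11.9%; Wald 2.9, 3.9 and 4.5%; Firth 4.5, 4.8 and 3.9%.

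Sensitivity with confounding (assumed: continuous covariates shifted 0.3 SD between groups, two of them prognostic at log odds ratio 0.5 per SD; conditional odds ratio 0.41): ML 0.39, 0.35 and 0.27, with ordinary profile coverage 93, 91 and 86%; Firth 0.42 throughout, with coverage 95, 95 and 96%.

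**Smaller analysed set.** The 72 allows for drop-out, and Participants excludes caesarean births. With 12 Pilates women, the chance of no event at 2% is 0.98^12 = 78%.

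**The case against.** The strongest reply is that Wald failure needs several things the documents do not establish: that Wald intervals are used at all, that the outcome is episiotomy, that group is in the model, and that the very low Pilates rate is met. That stands. A reader might infer that the planned interval will fail; the documents support only a conditional statement. By a 15% Pilates rate the empty cell is down to 2% of trials, and with no empty cell Wald coverage is about 96 to 97% from 5% upward.

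A reader might also infer that the model is bound to exaggerate the effect. That depends on a long list, and 12 is an assumed number. With the six baseline variables the shift (0.37 against 0.41) is small beside the sampling error of 24 versus 48, and Wald coverage is 95%. Nor do these any-injury results show inflated Wald type I error.

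The plan describes the models as a search for associated variables, so their role as protection against confounding is the reader's inference. It is fair only in that nothing else is adjusted. The group comparison also has Fisher's test, whose power at the planning rates with 24 versus 48 is above 99.9%.

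Lastly, an ordinary profile interval might seem a sufficient repair. It is not: on the three-covariate any-injury model it covers slightly less than Wald (94% against 96%), and at 10% versus 51% it covers about 90 to 91%.

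**Conclusion.** The concern holds in conditional form. The one adjusted analysis is left open in its predictors, group term and interval method, in a sample where those choices matter.

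- **Episiotomy with group as a term:** at the plan's own rates the ordinary estimate has no finite log odds ratio in 62% of trials, falling to 2% at a 15% Pilates rate. These figures are exact given the rates and 24 versus 48.
- **Any injury:** the risk is overfitting. It is material with an assumed 12 covariates (0.30 against 0.41; ordinary profile coverage 87%) and minor with six. These figures rest on the assumed 85% background, the assumed Pilates rates and the simulated covariates.

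Firth penalised-profile intervals held 95 to 96% coverage in the simulated scenarios shown and 95 to 97% in the exact enumeration. The change is worth making, but the unadjusted comparison does not depend on it. Firth does not itself remove confounding.

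**What to change.** In Data analysis, once the binary outcome is named:

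1. State that the group comparison is a logistic model with study group plus a few pre-specified baseline covariates already available, for example age, BMI and district. Add parity if it is recorded: the Introduction links it to episiotomy and tears, but Outcomes does not list it.
2. Exclude childbirth variables that arise after the intervention, such as labour onset, type of delivery and analgesia.
3. Fit by Firth penalised likelihood, with a penalised-profile 95% interval and a penalised likelihood-ratio test for group. Firth with a Wald interval is not enough: its coverage was 91 to 94% at 2% versus 51%.
4. Report an ordinary profile or exact upper limit only as a supplement when a cell is empty.
5. Amend the sentence confining all calculations to SPSS 25.0 so that it names the software for the penalised fit.

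The cost is wording, with no new data unless parity has to be collected. The downsides are slight shrinkage of the odds ratio, a wider upper limit when a cell is empty (0.16 against 0.09 in the 0/24 example) and fewer exploratory predictors.

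### One unadjusted 5% level covers every analysis, so the two perineal outcomes alone carry about an 8–10% chance of a false group difference, and more if all six birth variables are compared

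*Combined protocol and SAP*

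**What the plan says.** The Data analysis section closes with one significance rule for the whole study: "In all statistical analyses, alpha will be set to below 5% / the significance level was established at 5"%. It follows a list of methods: t-tests, chi-square or Fisher tests, repeated measures ANOVA, Pearson correlations, non-parametric counterparts, and logistic models that "will be calculated in order to determine association of the variables with perineal trauma in childbirth". No section ranks these analyses, divides the 5%, corrects for their number or calls any of them exploratory.

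The Aim is to "evaluate the influence of Pilates sessions during pregnancy on the incidence and degree of intrapartum perineal injuries", which is already two questions. The Outcomes section lists six variables collected after birth: weeks of pregnancy at birth, labour onset, type of delivery, analgesia, episiotomy and degree of tear. Part of that list reads "Labour onset (spontaneous, stimulated, induced), type of delivery (spontaneous, assisted delivery with forceps, Thierry's spatulas or vacuum extraction, caesarean section". The Sample size section rests on one of the six, avoidance of episiotomy.

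**The concern.** A 5% level holds the error rate of one test at 5%. It does not hold 5% for the claim that the Pilates programme changes perineal outcomes when either of two results could support that claim. As written, a p-value just under 0.05 for episiotomy alone, or for tear degree alone, meets the plan's criterion. So does one for any other birth variable compared between the groups. The non-parametric versions are to be run as well, so one comparison can also yield two p-values, with no rule for which one counts.

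At stake is how an isolated significant result is read. The plan states 5%, but the false-positive rate for the family of claims it leaves open is higher.

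**Working it through.** **1. The plan's own figure.** The Sample size section asks for 80% power at 95% confidence. Its planning rates are given as "considering 49% avoiding episiotomy in the control group in comparison with 98% in the experimental group". Allocation is set at "a ratio of 2 women in the control group for every woman in the experimental group". Using the pooled two-proportion formula with p₁ = 0.98, p₂ = 0.49, r = 2 and p̄ = (0.98 + 2 × 0.49)/3 = 0.6533:

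n₁ = [1.960 × √(0.6533 × 0.3467 × 1.5) + 0.8416 × √(0.98 × 0.02 + 0.49 × 0.51/2)]² / 0.49² = (1.142 + 0.320)² / 0.2401 = 8.91.

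With the continuity correction: (8.91/4) × [1 + √(1 + 3/(8.91 × 0.49))]² = 11.8, rounded up to 12. That gives 12 + 24 = 36 women, the stated minimum. The study is therefore sized on a single two-sided 5% test of episiotomy. The planned total is larger: "the final number of participants will be 72, of which 24 will be from the experimental group and 48 the control".

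**2. Two perineal outcomes, each at 5%, no effect on either.**
- Independent tests: 1 − 0.95² = 9.8%.
- Simulated normal test statistics with a common correlation: 9.1% at 0.5 and 7.8% at 0.8.
- A null simulation at 24 versus 48 women (Fisher test for episiotomy, rank test for tear degree, assumed event rates, independent outcomes) gave about 8%. It falls below 9.8% because exact tests on small tables use less than their nominal 5%.

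**3. Six birth variables, if all are compared between groups.** Independent tests give 1 − 0.95⁶ = 26.5%. Simulation with a common correlation gives:

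| Assumed correlation | At least one p < 0.05 |
|---|---|
| 0 | 26.5% |
| 0.3 | 24.1% |
| 0.5 | 20.7% |
| 0.7 | 16.4% |
| 0.8 | 13.9% |

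The normal model stands in for a mix of tests. As a check, take independent outcomes with one t-test and five two-by-two tables at 24 versus 48, and assumed event rates of 10–50%. The rate is 18.1–22.2% if all five tables use Fisher's test and 24.1–28.3% if all use chi-square.

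**4. What control costs in power.** Holm over two tests compares the smaller p-value with 2.5% and, if that is significant, the larger with 5%. It holds the overall rate at or below 5% whatever the correlation. Exact Fisher power for episiotomy at the planning rates:

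| Women | α = 5% | α = 2.5% |
|---|---|---|
| 12 + 24 | 92.1% | 82.7% |
| 24 + 48 | 99.95% | 99.8% |

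The formula in step 1 is more conservative than the exact calculation. With 2.241 in place of 1.960 it gives 13.9, so 14 + 28 = 42 women, still well inside 72. No power can be given for tear degree, because the documents state no rates for it.

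**The case against.** The strongest reply is that the study already has a focus. The hypothesis in Background, the Aim and the Sample size section all point to perineal injury. In a 72-woman quasi-experimental study with a convenience sample, strict error control over secondary outcomes is partly a matter of taste. Naming a primary outcome would do much of the work. That is fair, and it limits the weight of the point. It does not remove it: with episiotomy named as primary, the rule for all analyses would still stand, and tear degree, also part of the aim, would still be claimable at the full 5%.

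A reader might also infer more than the documents support:

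- **A flat 21%.** That figure needs six tests and an assumed correlation of about 0.5. The documents give no correlations, so only a range is defensible.
- **Six stated between-group tests.** The Outcomes section says only that the birth variables are measured. The bivariate tests are assigned by type of data, which implies the comparisons without stating them one by one. The Introduction names type of birth, forceps and epidural as risk factors, so delivery type and analgesia could serve as covariates instead.
- **Ten tests, by adding serial measures.** Which of these would be tested is a guess. The list includes age and a starting level of activity, and weight and BMI are nearly one variable in a woman of fixed height.
- **Regression predictors as false Pilates effects.** A chance association between trauma and any predictor other than study group is not a Pilates effect and is not counted here.
- **A plan to report isolated findings as programme effects.** The plan has no such reporting rule. It simply does not prevent it.

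**Conclusion.** The point holds in limited form. The plan applies 5% to every analysis with no order, correction or exploratory label, while its aim contains two perineal questions. For episiotomy and tear degree the family-wise rate is about 8–10%, up to roughly twice the stated level. If all six birth variables are compared, it is about 14–27%, depending on an assumed correlation between 0.8 and 0.

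These figures assume no effect on any outcome, each test run once, and equal correlation between tests. They describe chance error only. Allocation is not randomised, and no control of alpha removes the bias that this can bring. The change is a cheap improvement, not a condition for the study to be interpretable.

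**What to change.** In the Data analysis section, replace the blanket rule as follows.

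1. Limit confirmatory claims to two comparisons by study group: episiotomy yes/no, on which the study is sized, and degree of perineal tear.
2. Name one test for each in advance, for example Fisher's exact test and a rank test, with no duplicate parametric or non-parametric version.
3. Control the pair with Holm at an overall two-sided 5%. A fixed sequence starting with episiotomy is an alternative if the sponsor prefers it, but it makes tear degree, which the aim covers, depend on episiotomy, which the aim does not name.
4. Label all other between-group tests, the serial measures, the correlations and all logistic-regression odds ratios as exploratory, reported with 95% intervals and without significance claims. This includes the study-group odds ratio, unless it is itself named in advance as the confirmatory test.

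The cost is a few sentences, with no extra women or data. Isolated findings on other variables become hypothesis-generating, and the first confirmatory threshold tightens to 2.5%. At the planning rates, episiotomy power stays above the stated 80% even at the 36-woman minimum.
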